8.1.6 Solicited Adverse Event

A solicited AE is a protocol-specified AE about which the investigator (or designee) proactively asks the participants during a protocol-specified time period. Solicited AEs to be assessed for this study are local injection site events of pain, redness, and swelling at the injection site and systemic events of fever with oral temperature $\geq 38.0^{\circ}\text{C}$ ($\geq 100.4^{\circ}\text{F}$; if more than one temperature reading is taken, the highest reading obtained each day should be recorded), fatigue, chills, headache, myalgia, arthralgia, and nausea.

Solicited AEs will be recorded by the participants using a diary (electronic or paper) for seven days postvaccination.

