9.6.4 Safety Analyses

The safety of PXVX0317 in adults ≥ 65 years of age will be evaluated using solicited AEs occurring from IP administration on Day 1 until Day 8 and unsolicited AEs from Day 1 through Day 29, AESI, MAAEs, and SAEs through Day 183 End of Study Visit, and vital signs.

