9.6.4.2 Vital Signs

Pre- and post-IP administration vital signs data will be listed by participant, visit, and time point for each treatment group for the safety population.

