**AEs, solicited**, are defined as those collected in the electronic e-diary or paper diary. Solicited AEs include local (i.e., pain, redness, and swelling) and systemic reactions (i.e., fever, chills, fatigue, headache, myalgia, arthralgia, and nausea). *Solicited AEs were to be entered on Day 1 through Day 8; solicited AEs starting on Day 9 or later will be excluded from tabulations, with the exceptions of AESI and SAEs (see Section 9.2.2 for solicited events collection details).*

The denominator for solicited AE tables comprises only those participants with at least one diary observation (i.e., any non-missing values but excluding “Not done/unknown”), at least one diary observation for a given symptom, or at least one diary observation for a given day, as applicable. *Note that an elevated in-clinic temperature assessment as part of 30-min post-vaccination vital signs does not count as a solicited AE, as vital signs data are summarized separately.*

**AE, treatment emergent**. AE collection begins at Day 1 (baseline), the day of IP administration. AEs occurring after a participant has given informed consent, but before vaccination, are excluded from summaries. Only treatment-emergent AEs are summarized.

**AEs, unsolicited**, are defined as those AEs not listed in the e-diary or paper diary but collected in the EDC. *Unsolicited AEs were to be collected though Day 29 unless they were SAEs, AESI, or MAAEs; unsolicited AEs starting on Day 30 or later that are not SAEs, AESI, or MAAEs are excluded from tabulations (see Section 9.2.2 for solicited vs. unsolicited events).*

Age at screening visit is automatically calculated by EDC based on date of birth versus date of informed consent. Age at baseline (Day 1) is be summarized in all outputs.

**Age group strata** are defined as ages  $\geq 65$  to  $< 75$  and  $\geq 75$  years as randomized. Note that, if a participant is randomized into a stratum and their age is later corrected such that they

should have been placed into a different age stratum, the participant is analyzed according to the corrected age stratum for immunogenicity analyses.

**Analysis visits** are defined in Section [5.5](#).

**Analysis populations** are defined in Section [5.3](#).

**Baseline** is defined in Section [5.6](#). Change from baseline is defined as (value at post-baseline assessment – value at baseline).

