## **9.5 Vital Signs, Physical Findings and Other Variables Related to Safety**

### **9.5.1 Vital Signs**

Observed values in vital signs include temperature, blood pressure, respiratory rate, and heart rate at the screening visit and pre- and post-vaccination on Day 1. All vital sign records are displayed in the participant data listings.

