## APPENDIX I LIST OF TABLES, FIGURES, AND LISTINGS

Note the list of TFLs is a living document and subject to changes during the study.

Table	Title
Baseline	
14.1.1	Participant Enrollment by Site – Randomized Population
14.1.2	Analysis Populations – All Participants
14.1.3	Participant Disposition – Randomized Population
14.1.4.1	Demography – Randomized Population, Both Ages Pooled and by Age Group
14.1.4.2	Demography – Safety Population, Both Ages Pooled and by Age Group
14.1.4.3	Demography – Modified Intent-to-treat Population, Both Ages Pooled and by Age Group
14.1.4.4	Demography – Immunogenicity Evaluable Population, Both Ages Pooled and by Age Group
14.1.5	Medical History – Randomized Population
14.1.6	Timing of Blood Sample Collection – Randomized Population
14.1.7.1	Important Protocol Deviations – Randomized Population
14.1.7.2	Reasons for Exclusion from Analysis Populations – Randomized Population
14.1.8.1	Prior and Concomitant Medications by Descending Frequency within ATC Class and Drug Name – Safety Population
14.1.8.2	Concomitant Vaccines by Descending Frequency within ATC Class and Drug Name – Safety Population
Immunogenicity	
14.2.1.1.1	Anti-CHIKV SNA Seroresponse Rate by Treatment Group and Visit – Immunogenicity Evaluable Population, Both Ages Pooled and by Age Group
14.2.1.1.2	Anti-CHIKV SNA Seroresponse Rate by Treatment Group and Visit – Immunogenicity Evaluable Population, Both Ages Pooled by Sex Subgroups
14.2.1.1.3	Anti-CHIKV SNA Seroresponse Rate by Treatment Group and Visit – Immunogenicity Evaluable Population, Both Ages Pooled by Race Subgroups
14.2.1.1.4	Anti-CHIKV SNA Seroresponse Rate by Treatment Group and Visit – Immunogenicity Evaluable Population, Both Ages Pooled by Ethnicity Subgroups
14.2.1.1.5	Anti-CHIKV SNA Seroresponse Rate by Treatment Group and Visit – Immunogenicity Evaluable Population, Both Ages Pooled by Baseline Serostatus Subgroups
	Note: Only needed if baseline seropositive rate is <math>\geq 10\%</math>.
14.2.1.2.1	Anti-CHIKV SNA Seroresponse Rate by Treatment Group and Visit – mITT Population, Both Ages Pooled and by Age Group
14.2.1.2.2	Anti-CHIKV SNA Seroresponse Rate by Treatment Group and Visit, Sensitivity Analyses – mITT Population, Both Ages Pooled and by Age Group
14.2.2.1.1	Anti-CHIKV SNA GMT by Treatment Group and Visit – Immunogenicity Evaluable Population, Both Ages Pooled and by Age Group

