16.2.7.2.2	Unsolicited Adverse Events Occurring Postvaccination on Day 1
16.2.7.3	Verbatim to Preferred Term Mapping for Unsolicited Adverse Events
16.2.7.4	Participant Identification of Adverse Events
16.2.8.1	Vital Sign Results
16.2.8.2	Physical Examination Results
16.2.8.3	Viral Screening Results
16.2.8.4	Hospitalization Details
16.2.8.5	Death Details

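### The SAP keeps an in-clinic post-dose fever out of the solicited AEs by pointing to a vital-sign summary, but only a participant listing of vital signs is planned

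*SAP*

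**What the plan says.** SAP 6.3 (Derived Variables, solicited AEs) takes solicited AEs from the electronic or paper diary. It adds that an elevated temperature measured in clinic at the 30-minute post-vaccination "vital signs does not count as a solicited AE, as vital signs data are summarized separately". SAP 9.2.2 repeats the rule with the same reason. The SAP's summary of changes shows that the exclusion came in with version 2.0.

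The output planned for vital signs is described in three places:

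- SAP 9.5.1: "All vital sign records are displayed in the participant data listings".
- Protocol 9.6.4.2: "Pre- and post-IP administration vital signs data will be listed by participant, visit, and time point for each treatment group for the safety population".
- SAP Appendix I: one entry, Listing 16.2.8.1, titled "Vital Sign Results".

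Protocol 9.6.4 counts vital signs among the data used to evaluate safety; its list ends with "SAEs through Day 183 End of Study Visit, and vital signs". The opening sentence of SAP Section 9 says that all safety data are presented both as tabulations and as participant listings.

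**The concern.** The exclusion rests on one stated reason, and that reason refers to an output that neither document plans. A reader of SAP 6.3 would expect a measured post-dose fever to be visible by arm somewhere other than the solicited tables. As the plan stands, the reading is visible by arm only to someone who goes through the listing row by row.

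The safety of the vaccine is a coprimary objective, and Protocol 1.7 says that the vaccine has not been evaluated before in this age group. The post-dose set is the only scheduled vital-sign assessment after injection (Protocol Table 1). The same gap covers pulse, blood pressure and respiratory rate. Protocol Appendix I grades all of these, but the SAP plans no by-arm summary of them, and the SAP's own grading appendix contains only fever among them.

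**Working it through.** There is no plan figure to reproduce. The check compares the passages and counts the planned outputs.

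**1. Is there a vital-sign summary?** The titles in SAP Appendix I were read from Table 14.1.1 to Table 14.3.5.12, followed by all figures and listings.

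| Output type | Vital-sign outputs |
|---|---|
| Tables | 0 |
| Figures | 0 |
| Listings | 1 (16.2.8.1) |

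SAP 6.2 has rounding rules for vital-sign means and standard deviations. These set a format for statistics but plan no output.

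**2. Can the clinic reading enter an AE table under the SAP's definitions?**

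- *Solicited:* no. SAP 6.3 and 9.2.2 exclude it by name.
- *Unsolicited:* not clearly. SAP 6.3 defines unsolicited AEs as those that are not diary items, and fever is a diary item. SAP 9.2.2 and 9.2.3 move diary-type events into the unsolicited set when they are still ongoing after Day 8, serious, medically attended or AESI. A brief fever on Day 1 would usually meet none of these.
- *Day 1 AEs:* SAP 9.3.6 plans a listing (16.2.7.2.2), not a table.

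**3. Which other routes remain for the same fever?**

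- *Diary:* Protocol 3.2.9 has participants record their highest daily temperature. A fever still present when the participant measures on Day 1 would count as solicited.
- *Investigator-entered AE:* Protocol 8.1.7 lets an unsolicited AE be one that the investigator finds, and Protocol 6.3 schedules AE evaluation after dosing on Day 1. If entered and classified as unsolicited, it would reach the by-arm tables 14.3.5.x and 14.3.3.1.

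The first route depends on what the participant does. The second depends on what the site does and on a classification that the SAP leaves open.

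**4. Size.**

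- Post-dose sets affected: 2 arms × 200 = 400, at the planned enrolment.
- Fevers at 30 to 60 minutes: no rate is given. Assuming 0-1%, the count is 0 × 200 = 0 to 0.01 × 200 = 2 per arm.

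**The case against.** The best defence is that the protocol chose a listing for vital signs and the SAP follows it. Vital signs are not among the safety endpoints in Protocol 3.3.1 or SAP 3.2. The listing is arranged by treatment group, so a handful of fevers could be counted by hand. The Appendix I list can also change: "Note the list of TFLs is a living document and subject to changes during the study".

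Much of this stands. Listing vital signs is not in itself a departure from the protocol, and the count is likely to be small. It does not rescue the stated reason, however. A listing has no counts or percentages by arm, and a table that could be added later is not a planned one.

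A reader might also draw three stronger conclusions that the documents do not support.

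- *That such a fever is certain to be lost.* The rule excludes the clinic reading from the solicited AEs. It does not bar the fever itself from every table. The diary and investigator routes remain possible, and SAP 9.2.2 and 9.2.3 show that a diary-type event can be recorded as unsolicited.
- *That the SAP contradicts Protocol 8.1.6.* That section says "if more than one temperature reading is taken, the highest reading obtained each day should be recorded". It also says that participants record solicited AEs in the diary, and Protocol 3.2.9 places the highest-reading rule there. It is a diary instruction and does not require staff readings to feed the solicited endpoint.
- *That the clinic reading should therefore be counted as solicited fever.* The solicited tables use as denominator only participants with some diary data. Adding clinic readings would mix two collection methods and could put a person in the numerator who is not in the denominator.

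**Conclusion.** The point holds as an internal inconsistency: the exclusion in SAP 6.3 and 9.2.2 relies on a vital-sign summary that is not planned. As a result, the site reading enters no planned by-arm table unless the participant or the investigator also reports the fever, and the SAP assures neither.

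The effect on fever counts is small, 0-2 per arm on the assumed 0-1%. That range is an assumption, since the documents give no rate. The lack of a by-arm view of about 400 graded post-dose sets of pulse, blood pressure and respiration is the wider consequence, though it reflects the protocol's choice of a listing rather than an SAP error. No immunogenicity result is affected. The change should be made because it is cheap and serves a coprimary safety objective.

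**What to change.** 1. Keep solicited fever diary-based, as SAP 6.3 now has it.
2. Add to SAP 9.5.1 and Appendix I one by-arm table for the safety population. It should show pre-dose, post-dose and change values for each vital sign, the number and percentage with a post-dose oral temperature of at least 38.0 °C, and the post-dose grade by Protocol Appendix I. The table must cite the protocol's scale, because SAP Appendix II does not grade pulse, blood pressure or respiratory rate.
3. State in SAP 6.3 that an in-clinic fever which the investigator enters as an AE is tabulated with the unsolicited AEs.

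The cost is one extra table from data already collected and a sentence of SAP text. A few more fevers may be shown. With the table in place, the reason given in SAP 6.3 and 9.2.2 becomes true as written.

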## 6.4 Statistical Hypotheses

### 6.4.1 Coprimary Immunogenicity Endpoints

The study is a multicenter, randomized, two-arm, active-controlled study to evaluate PXVX0317 vaccine vs. placebo. A successful trial means success on each of the coprimary endpoints: seroresponse ( $H_{A1}$ ) and GMT ( $H_{A2}$ ), both at Day 22 using the IEP. Statistical hypotheses for each of these endpoints are discussed in turn in this section. The familywise error rate is fixed at a two-sided alpha of 0.05 by the requirement that both coprimary endpoints must be met for a successful outcome.

In standard statistical notation, the null and alternative hypotheses are:

$H_0$ :  $H_{A1}$  not met or  $H_{A2}$  not met

$H_A$ :  $H_{A1}$  met and  $H_{A2}$  met

where  $H_{A1}$  and  $H_{A2}$  are the alternative hypotheses for each of the coprimary endpoints as defined below in this section.

The first coprimary endpoint is the treatment group-specific estimates and difference between treatment groups in anti-CHIKV SNA seroresponse rates using a titer of █ at Day 22 in the IEP for both age strata pooled and is tested in two ways. First, the lower bound of the Newcombe hybrid score method two-sided 95% CI on the difference in seroresponse rates between PXVX0317 and placebo must be █. Secondly, the null hypothesis of no difference between seroresponse rate percentages is tested using a two-sided chi-square test with alpha=0.05. In standard statistical notation, the null and alternative hypotheses for the first coprimary endpoint are as follows:

$H_01: (P_{PXVX0317} - P_{placebo}) \leq 0$  using a two-sided chi-square test  
 $H_{A1}: (P_{PXVX0317} - P_{placebo}) > 0$  using a two-sided chi-square test  
where  $P_{PXVX0317}$  is the percentage of PXVX0317 participants and  $P_{placebo}$  is the percentage of placebo participants with seroresponse at a titer of █ at 21 days after vaccination in the IEP for both age strata pooled.

The second coprimary endpoint tests for a significant difference in treatment group-specific Day 22 GMTs in the IEP for both age strata pooled, as derived from a one-sided alpha=0.025 ANOVA with  $\log_{10}$ -transformed anti-CHIKV SNA titers ( $\log_{10}$ ) as the dependent variable and treatment group and study site as the fixed effects. The adjusted least square means and their 95% CIs calculated based on the ANOVA are back transformed and reported as the group GMT values. In standard statistical notation, the null and alternative hypotheses are:

$H_02: (GMT_{PXVX0317} - GMT_{placebo}) \leq 0$   
 $H_{A2}: (GMT_{PXVX0317} - GMT_{placebo}) > 0$

where  $GMT_{PXVX0317}$  is the GMT 21 days after vaccination for IEP participants in both age strata pooled.

#### 6.4.2 Key Secondary Immunogenicity Endpoints

A prespecified hierarchical approach is employed for the seroresponse key secondary immunogenicity endpoints to preserve the type I error rate without the need for further multiplicity adjustment. If the null hypotheses are rejected for both coprimary endpoints, only then are the key secondary endpoints for the seroresponse rate difference ( $H_{A3}$ ) at Days 15 and 183 tested sequentially, in that order, each for the IEP across both age groups combined. At Days 15 and 183, the endpoint is tested for the success criterion of superiority to placebo using a two-sided chi-square test with alpha=0.05. When a nonsignificant test is reached formal testing stops, and the remaining endpoints are reported for information only.

1. Day 15 seroresponse at a titer of █, including superiority to placebo.
2. Day 183 seroresponse at a titer of █, including superiority to placebo.

In standard statistical notation, the null and alternative hypotheses are:

$H_{03}: (P_{PXVX0317} - P_{placebo}) \leq 0$  using a two-sided chi-square test for Day 15 and  $(P_{PXVX0317} - P_{placebo}) \leq 0$  using a two-sided chi-square test for Day 183

$H_{A3}: (P_{PXVX0317} - P_{placebo}) > 0$  using a two-sided chi-square test for Day 15 and  $(P_{PXVX0317} - P_{placebo}) > 0$  using a two-sided chi-square test for Day 183

After testing the coprimary immunogenicity endpoints and, if both met, the hierarchical key secondary immunogenicity endpoints, no other formal hypothesis testing is carried out. The remaining secondary immunogenicity endpoints involving GMTs, GMFI, other titers, the exploratory endpoint, and all safety endpoints are evaluated and reported for information only, thus no further Type I error control or multiplicity adjustment is needed.

## 6.5 Handling of Missing Data and Other Data Issues

Please see Section 6.3 for assumptions for AEs with missing relatedness and/or severity.

### 6.5.1 Missing or Partial Dates for Solicited Adverse Events

Solicited adverse events are collected from IP administration on Day 1 until Day 8 using an electronic diary (e-diary) or paper diary. In the case where a participant has all eight diary entries present and a single entry is missing a date (or has a partial date), then the missing date is assumed to be the date of the missing diary entry for that participant.

### 6.5.2 Missing or Partial Dates for Unsolicited Adverse Events and Concomitant Medications

Unsolicited AE collection begins at Day 1 (baseline), the day of IP administration.

***Consequently, all AEs will be considered treatment emergent regardless of onset date.***

For missing or partial dates for prior or concomitant medication/therapy, the following conventions are used for the purpose of determining whether the medication/therapy is concomitant or not. Original values are provided in the listings as is, without imputation.

- For start date missing completely or missing the year, impute the date to the date of first exposure to any study treatment.
- For start date missing both the month and the day, if the year is the same as the date of first exposure to any study treatment, impute the date to the date of first exposure to any study treatment, otherwise, impute the date to January 1st.
- For start date missing the day only, if the year and the month are the same as the date of first exposure to any study treatment, impute the date to the date of first exposure to any study treatment, otherwise, impute the date to the first of the month.
- For end date missing completely or missing the year, impute the date to the date of last contact.
- For end date missing both the month and the day, if the year is the same as the date of last contact, impute the date to the date of last contact, otherwise, impute the date to December 31st.
- For start date missing the day only, if the year and the month are the same as the date of last contact, impute the date to the date of last contact, otherwise, impute the date to the last day of the month.

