5.1.6 Investigational Product Preparation

On Day 1 before IP administration, the interim medical history (ie, from Screening Visit to Day 1) will be reviewed and updated in the participant file, a targeted physical exam may be performed, and blood samples will be collected. Immediately prior to IP administration, staff will verify that the participant is still eligible and randomize the participant in the EDC (Section 3.4.2). Once these procedures are performed and if the participant is still eligible, IP will be administered.

All doses of IP are 0.8 mL in volume and are administered by IM injection in the deltoid muscle with a 1 mL syringe and 25 gauge 1" (or 1.5", at the investigator's discretion) needle using universal precautions and sterile technique; see [Table 2](#) for more details.

Investigational product is to be administered only under the direct supervision of the PI or a qualified subinvestigator identified on the FDA Form 1572. The injection will be administered into the deltoid muscle by a staff member delegated by the investigator. Right or left deltoid muscle may be used at the discretion of the administering staff member with consideration for participant preference and features that may obscure interpretation of any local AEs such as tattoos, scars, or other lesions.

For further details see the Pharmacy Manual.

The investigator is responsible for maintaining accurate inventory records of IP (PXVX0317 or placebo). The investigator or designee will inventory all IP kit shipments upon receipt, acknowledge possession by signing all required documentation, and returning these to the sponsor. The investigator must ensure that all drug supplies are kept in a secure location in the site pharmacy in accordance with recommended storage conditions. Inventory and ongoing record of test material supplies using the Drug Accountability Form provided within the Clinical Trial Material Tracking Module of the sponsor's RTSM system. This inventory record for the IP will include:

- Protocol name, number, and sponsor
- Kit number
- Study site and investigator name
- Use-by/Expiry/Retest date
- Name and title of qualified individual administering IP.

These records will be reviewed by representatives of the sponsor and may be reviewed by regulatory agencies.

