6.3 Baseline, Randomization, and IP Administration (Visit 2, Day 1)

The following will take place during the visit and prior to IP administration:

- Reverification of eligibility criteria
- Review medical history
- Review prior and concomitant medications
- Vital signs
- Targeted physical examination (as needed)
- Blood collection for anti-CHIKV SNA and CHIKV antibodies to neutralize strains representing all CHIKV genotypes (Section 3.2.6)
- Randomization (Section 3.4.2)
- Confirm and review any AEs that may have occurred after ICF signing
- Diary or memory aid (electronic or paper) training, ruler and thermometer distribution and training (Section 3.2.9)
- IP administration (Section 3.2.7)

The following will take place during the visit and after IP administration:

- In-clinic acute observation (Section 3.2.8)
- Vital signs (Section 3.2.4)
- Solicited AEs, unsolicited AEs, MAAEs, SAEs and AESI evaluation (Sections 3.2.9, 3.2.10, 3.2.11)

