9.6.4.1 Adverse Events

Adverse events will be coded to the MedDRA dictionary SOC and PT. They will be graded for severity according to Section 8.1.8. Only treatment-emergent AEs will be collected (ie, those after the start of IP administration). Adverse events will be reported using both age strata pooled, but selected AE analyses will be repeated for the separate age strata. All AE tabulations and participant listings will be based on the safety population.

Solicited AEs, unsolicited AEs, MAAEs, AESI, and SAEs will be summarized separately by treatment group and SOC, PT, and maximum severity for the safety population for both age strata combined. Only participants with at least one solicited AE observation (ie, any nonmissing values but excluding “not done/unknown”) will be summarized. Solicited AEs continuing beyond seven days after IP administration will be combined with the unsolicited AEs; a combined summary table of solicited and unsolicited AEs by treatment group and SOC, PT, and maximum severity will also be provided for the safety population for both age strata pooled.

Additional AE displays will include the following:

- Solicited AEs \geq Grade 3
- Treatment-related (“possibly”, “probably” or “definitely”) solicited AEs
- Solicited AEs: day of first onset, duration, day postinjection, and occurrence of at least one solicited AE by category (local, systemic)
- Unsolicited AEs \geq Grade 3
- Treatment-related (“possibly”, “probably” or “definitely”) unsolicited AEs

- Medically attended AEs
- Treatment-related MAAEs
- AEs leading to study discontinuation
- Fatal AEs, if any
- Treatment-related (“possibly”, “probably” or “definitely”) SAEs

Separate participant data listings of solicited and unsolicited AEs sorted by participant identifier and AE start date will be generated. Diary compliance will not be summarized.

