### **9.2 Adverse Events**

The safety of PXVX0317 in healthy adult participants  $\geq 65$  years of age is evaluated using solicited AEs occurring from IP administration on Day 1 through Day 8, unsolicited AEs through Day 29, and AESI and SAEs and MAAEs through Day 183 EOS. AEs are coded to SOC and PT according to the MedDRA dictionary per Section 5.8. They are coded for severity according to Section 5.9 and Appendix II. Only treatment-emergent AEs are summarized (i.e., excluding those after a participant has given informed consent, but before vaccination). See Section 6.3 for definitions.

Solicited AEs, unsolicited AEs, AESI and SAEs and MAAEs are summarized separately by treatment group and maximum severity for the safety population for both age strata combined. Separate participant data listings of solicited and unsolicited AEs sorted by participant identifier and AE start date are generated.

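### SAP 6.5.2 calls every AE treatment-emergent whatever its onset date, against SAP 6.3, SAP 9.2 and Protocol 9.6.4.1, and the SAP does not say which rule governs

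*SAP*

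**What the plan says.** SAP 6.5.2, the section on missing or partial dates for unsolicited AEs and concomitant medications, opens with a premise: "Unsolicited AE collection begins at Day 1 (baseline), the day of IP administration". From this it concludes, in emphasised type, that "all AEs will be considered treatment emergent regardless of onset date". The date conventions that follow in that section are for medications and therapies only.

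Three other places say something different:

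- SAP 6.3, in the definition of a treatment-emergent AE: "AEs occurring after a participant has given informed consent, but before vaccination, are excluded from summaries".
- SAP 9.2, which governs the AE tables, summarises only treatment-emergent AEs and describes this as "excluding those after a participant has given informed consent, but before vaccination".
- Protocol 9.6.4.1: "Only treatment-emergent AEs will be collected (ie, those after the start of IP administration".

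Two protocol sections bear on whether pre-dose events can be recorded at all. Protocol 6.3 lists, among the Day 1 tasks before IP administration: "Confirm and review any AEs that may have occurred after ICF signing". Protocol 5.1.6 says that before dosing "the interim medical history (ie, from Screening Visit to Day 1) will be reviewed and updated in the participant file".

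**The concern.** SAP 6.3 and SAP 6.5.2 start from the same fact, that AE collection begins on Day 1, and reach opposite rules. An AE with a documented onset before the injection is out under one and in under the other.

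The premise does not carry the conclusion in 6.5.2. Day 1 is a calendar day and includes time before the injection. The Day 1 visit also reviews AEs since consent before dosing, and the screening window can run to 30 days. The exclusions in 6.3 and 9.2 would be unnecessary if pre-dose AEs could not arise.

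What is at stake is which events are counted by arm in the safety tables. Evaluation of safety is one of the coprimary objectives. Events that began before vaccination cannot be caused by it, so counting them would raise both arms' rates and blur the contrast.

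There is also a gap. Protocol 9.5 leaves the rules for partial or missing dates to the SAP. For treatment emergence of unsolicited AEs, the disputed sentence is all that 6.5.2 supplies.

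**Working it through.** The plan gives no figure on this point, so there is none to reproduce. The check compares the texts and then works out a scale.

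**Step 1: the rules applied to the same event.**

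- *Known onset before IP administration, entered on the AE eCRF.* SAP 6.5.2: treatment-emergent. SAP 6.3 and 9.2: excluded from summaries. Protocol 9.6.4.1: not treatment-emergent. The rules conflict.
- *Known onset after IP administration.* All four agree that it is treatment-emergent.
- *Missing or partial onset.* SAP 6.5.2: treatment-emergent. The other three give no rule for an unresolved date, so 6.5.2 fills a gap here.
- *Day 1 onset with no recorded time.* SAP 6.5.2: treatment-emergent. The others turn on whether onset came before or after the injection, which such a record cannot show. SAP 9.3.6 calls for a listing of AEs after vaccination on Day 1, so the plan does intend to separate the two parts of that day.

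No sentence in the SAP ranks 6.5.2 against 6.3 or 9.2.

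**Step 2: scale if 6.5.2 were applied literally.**

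Input from the documents: 200 participants planned per arm (SAP 2.2).

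Effect on one arm's rate of one participant whose only AE was pre-dose: 1/200 = 0.005, or 0.5 percentage points.

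Effect on the contrast: let p1 and p0 be the post-dose AE rates for vaccine and placebo. Let q be the share of each arm with a pre-dose event on the AE eCRF, assumed equal in both arms and independent of later AEs.

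- Tabulated rate in an arm: 1 − (1 − p)(1 − q) = p + q(1 − p)
- Tabulated risk difference: [p1 + q(1 − p1)] − [p0 + q(1 − p0)] = (p1 − p0)(1 − q)

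The true difference is therefore multiplied by (1 − q). The documents give no q, so these values are assumptions:

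- q = 0: factor 1.00 (no effect)
- q = 1%: factor 0.99
- q = 5%: factor 0.95
- q = 10%: factor 0.90

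**The case against.** The strongest reply is that the intended meaning is clear. The sentence sits under a heading about missing or partial dates and reads naturally as a default for onsets that cannot be resolved. SAP 6.3 is the definition and SAP 9.2 is the table specification; both exclude pre-dose events, and 9.2 refers to 6.3 for definitions. A programmer would have to put a data-handling sentence above both.

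There are upstream limits too. Under Protocol 9.6.4.1 only events after the start of IP administration are to be collected. The schedule of events shows no AE collection at screening. Events between screening and Day 1 can be recorded as interim medical history, and SAP 6.3 treats medical history items as predating the study. Protocol 6.3 asks sites to review AEs since consent; it does not say they are entered on the AE eCRF. Solicited AEs, collected from IP administration, are largely outside the problem. All safety endpoints are reported for information only.

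Much of this stands. It limits how often the conflict could matter, and it rules out any effect on a formal test. It does not remove the conflict. The sentence covers all AEs and any onset date, so its words reach known pre-dose dates. The medical-history route covers only what is entered on that form, and Protocol 6.3 lists AE review as a separate task. A prespecified plan should not leave the choice between two rules to the programmer.

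A reader might infer that the plan puts pre-vaccination events into the safety tables. The documents do not support that. It would require both that such an event is entered on the AE eCRF and that 6.5.2 is followed over the explicit exclusions in 6.3 and 9.2.

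**Conclusion.** SAP 6.5.2 is wrong as written. It states a rule that would misclassify AEs with a known pre-dose onset, it conflicts with two other SAP sections and with the protocol, and the SAP does not say which prevails.

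The consequence is conditional and probably small. It depends on the number of pre-dose events that reach the AE eCRF, which the documents do not give, and on the (1 − q) result's assumptions of equal q in both arms and independence from later AEs. Equality is reasonable in expectation, because these events precede a blinded, randomised injection.

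Two stronger readings should be resisted. One is that the safety comparison is materially diluted: that needs a sizeable q, for which the documents offer no evidence. The other is that the rule favours one arm: the expected effect is to raise both rates and shrink any difference in either direction. No immunogenicity endpoint, success criterion or hypothesis test is affected.

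**What to change.** Replace the sentence in SAP 6.5.2 with:

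> An AE with a missing or partial onset date, or a Day 1 onset with no recorded time, is considered treatment-emergent unless the available date parts, the stop date or the eCRF record show that it began before IP administration. AEs with a known onset before IP administration are not treatment-emergent and appear in listings only (see Section 6.3).

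This brings 6.5.2 into line with SAP 6.3, SAP 9.2 and Protocol 9.6.4.1. It supplies the missing-date rule for treatment emergence that Protocol 9.5 leaves to the SAP. The Day 1 clause is needed because the documents do not establish that AE onset time is recorded; without a time or other evidence, the event stays in the tables, which is the cautious choice for safety.

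The cost is one replaced SAP passage and one programming rule, settled before unblinding. No new data are needed, and the protocol text need not change.
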